17.1.3. WORK PRODUCTIVITY AND ACTIVITY IMPAIRMENT QUESTIONNAIRE – ULCERATIVE COLITIS

The Work Productivity and Activity Impairment Questionnaire – Ulcerative Colitis (WPAI-UC) consists of 6 questions asking about the effect of UC on the subject's ability to work and perform regular activities.

The percent work time missed due to problem (absenteeism), percent impairment while working due to problem (presenteeism), percent overall work impairment due to problem, and percent activity impairment due to problem are derived on the eCRF directly. Details about derivations can be found in [APPENDIX 7](#).

17.1.4. URGENCY NUMERIC RATING SCALE [NRS]

The urgency NRS is a single item that measures the severity for the urgency (sudden or immediate need) to have a bowel movement in the past 24 hours using an 11-point NRS ranging from 0 (no urgency) to 10 (worst possible urgency).

17.1.5. ABDOMINAL PAIN NRS

The abdominal pain NRS is a single item that measures the “worst abdominal pain in the past 24 hours” using an 11-point NRS ranging from 0 (no pain) to 10 (pain as bad as can imagine).

17.1.6. UC-RELATED HOSPITALIZATIONS AND SURGERIES

The UC-related hospitalizations will be captured on the Adverse Event eCRF. The UC-related surgeries, including colectomy, are captured on the Non-Drug Treatment eCRF. Blinded review of AE preferred terms will be performed to determine UC-related hospitalizations.

The UC-related surgeries, including colectomy, will be captured on the Concomitant Non-Drug Treatment eCRF.

17.2. MISSING DATA METHODS

No missing data will be imputed for HRQoL endpoints.

18. Safety Outcomes

All safety outcomes will be based on the Safety Analysis Set. There will be no statistical comparisons between the treatment groups for safety data, unless otherwise specified.

18.1. Adverse Events

Adverse Events (AEs) will be coded using MedDRA (version 24.1). The version used to code AEs will be displayed in the analyses. Treatment emergent adverse events (TEAEs) are defined as AEs that started or worsened in severity on or after the first dose of study treatment in Study APD334-308.

An event that was on-going at end of APD334-302 will be reported in APD334-308 only if it became worsened (increase in severity) after the first dose of study treatment in Study APD334-308. In an integrated report combining APD334-302 and APD334-308 data, this event will be counted only once.

Refer to APPENDIX 2 for handling of partial dates for AEs for the purpose of assigning treatment-emergent flags. In the case where it is not possible to define an AE as treatment emergent or not, the AE will be classified as treatment emergent.

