9.5. Follow-Up Period

For subjects not participating in the OLE study, a follow-up visit will be performed at 2 and 4 weeks after the last dose of study treatment as indicated in the Schedule of Assessments (Table 7).

If the Early Termination or Study Completion visit is ≥ 2 weeks after the last dose of study treatment, the 2-Week Follow-Up visit is not required; however, the 4-Week Follow-Up visit should be scheduled and completed. If the Early Termination or Study Completion visit is ≥ 4 weeks after the last dose of study treatment, the 4-Week Follow-Up visit is not required.

If the absolute peripheral lymphocyte count is not within normal limits at the 4-Week Follow-Up visit, subjects should return for complete blood count (CBC) with differential according to local standard of care (captured as subsequent follow-up visit or unscheduled visit).

All adverse events should be recorded for 30 days after last dose of study treatment (Section 9.8.8.2.2).

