9.8.8.2.2. Recording Adverse Events

The adverse event reporting period for safety surveillance begins when the subject is initially included in the study (date of first signature of informed consent) and continues up to 30 days after the last study treatment administration. If an adverse event is not resolved or stabilized by this time, the Sponsor in consultation with the Investigator will decide whether to continue to monitor the adverse event or closeout the event in the database if no further follow-up is necessary.

Any SAE suspected to be related to the study treatment must be reported whenever it occurs, irrespective of the time elapsed since the last administration.

Investigators and study personnel will record all adverse events and SAEs whether received through an unsolicited report by a subject, elicited during subject questioning, discovered during physical examination, laboratory testing, and/or other means by recording them on the eCRF and/or SAE Form, as appropriate. The following information should be recorded on the adverse event eCRF:

- Description including onset and resolution dates
- Whether it met SAE criteria
- Severity
- Relationship to study treatment or other causality
- Outcome

For SAEs, events occurring secondary to the primary event should be described on the eCRF in the narrative description field.

The following should be considered when recording SAEs:

- Death is an outcome of an event. The event that resulted in the death should be recorded and reported on the eCRF.
- For hospitalizations, surgical, or diagnostic procedures, the illness leading to the surgical or diagnostic procedure should be recorded as the SAE, not the procedure itself. The procedure should be captured in the narrative as part of the action taken in response to the illness.

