- P Pharmacokinetic blood samples are to be collected predose (within the 60-minute period prior to dosing). A PK sample should be taken, if possible, at the time of any SAE or AE leading to study treatment discontinuation. In addition, for subjects not enrolling into the APD334-303 study, a blood sample for PK should be drawn at the 2-Week and 4-Week Follow-Up visits. For all PK blood draws, the time of the last dose should be documented.
- 4 Blood samples for biomarkers should be collected on the indicated day prior to the daily dose as applicable.
- ^r All concomitant medications and procedures should be collected through the safety reporting period (Section 6.7). For subjects who received corticosteroid therapy during the APD334-302 study, corticosteroids should be tapered entering this study (Section 6.7.2.2).
- S QuantiFERON TB Gold and tuberculin skin test should not be performed in subjects previously diagnosed with TB infection. The TB questionnaire will be completed at every study visit for subjects receiving TB prophylaxis therapy.
- ^t Study treatment should be dispensed as indicated. For subjects who consent and are eligible for the APD334-303 OLE study prior to Week 52, double-blinded study treatment may be dispensed in the event there is a gap between the last on treatment visit of Study APD334-308 and W0/D1 of the OLE. Study treatment may be dispensed at Week 52 if the subject qualifies for and has opted to participate in the APD334-303 OLE study but who do not enter the OLE study on the same day as their Week 52 visit.
- ^u On days with scheduled study visits, subjects should not take their dose of study treatment at home in order to complete predose study procedures. The dose will be taken at the study site after all predose assessments and procedures have been completed. At the Week 12 visit, subjects should take study treatment after confirmation of eligibility and enrollment into Study APD334-308.

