18.1.1. All TEAEs

All TEAEs will be summarized by SOC and PT and presented by descending frequency in the etrasimod group. All AEs, regardless of treatment-emergent status, will be included in an AE listing. Additionally, a listing of other AE details as collected on the CRF will be presented.

Exposure-adjusted incidence rate (EAIR) of TEAEs will be summarized by SOC and PT. Exposure is defined as the sum of either time (year) from first dose in Study APD334-308 to the onset of first such event for those who experienced this AE in Study APD334-308, or time (year) from first dose in Study APD334-308 to last participation for those who did not experience this AE. The EAIR is calculated as the number of subjects with the AE divided by the total exposure in subject-years.

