APPENDIX 2. PARTIAL DATE CONVENTIONS

Imputed dates will NOT be presented in the listings.

ALGORITHM FOR TREATMENT EMERGENCE OF ADVERSE EVENTS IN STUDY APD334-308:

START DATE	STOP DATE	ACTION
Known	Known/Partial/ Missing	If start date < study drug first dose date in APD334-308, then not TEAE If start date < study drug first dose date in APD334-308 AND event worsened (increase in severity) after first dose date in APD334-308, then TEAE If start date >= study drug first dose date in APD334-308, then TEAE
Partial, but known components show that it cannot be on or after study drug first dose date in APD334-308	Known/Partial/ Missing	Not TEAE
Partial, could be on or after study drug first dose date in APD334-308 OR Missing	Known	If stop date < study drug first dose date in APD334-308, then not TEAE If stop date >= study drug first dose date in APD334-308, then TEAE
	Partial	Impute stop date as latest possible date (i.e. last day of month if day unknown or 31st December if day and month are unknown), then: If stop date < study drug first dose date in APD334-308, then not TEAE If stop date >= study drug first dose date in APD334-308, then TEAE
	Missing	Assumed TEAE

START DATE	STOP DATE	ACTION

ALGORITHM FOR PRIOR / CONCOMITANT MEDICATIONS:

Start Date	Stop Date	Action
Known	Known	
If medication stop date < study med first dose date in APD334-308, assign as prior
 
If medication stop date \geq study med first dose date in APD334-308, assign as concomitant

	Partial	
Impute stop date as latest possible date (ie, last day of month if day unknown or 31st December if day and month are unknown), then:
 
If medication stop date < study med first dose date in APD334-308, assign as prior
 
If medication stop date \geq study med first dose date in APD334-308, assign as concomitant

	Missing	If medication stop date is missing could never be assumed a prior medication, assign as concomitant
Partial	Known	
Impute start date as earliest possible date (ie, first day of month if day unknown or 1st January if day and month are unknown), then:
 
If medication stop date < study med first dose date in APD334-308, assign as prior
 
If medication stop date \geq study med first dose date in APD334-308, assign as concomitant

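### The TEAE window has a start but no end, so events recorded in APD334-308 after roll-over to open-label etrasimod would be tabulated as placebo TEAEs for former placebo subjects

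*SAP*

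**What the plan says.** **Start of the window.** SAP Section 18.1 counts "AEs that started or worsened in severity on or after the first dose of study treatment in Study APD334-308". The SAP Appendix 2 algorithm codes the same test: "If start date >= study drug first dose date in APD334-308, then TEAE". Neither compares the event date with the last 308 dose or the first APD334-303 dose. Doubtful cases go one way: "In the case where it is not possible to define an AE as treatment emergent or not, the AE will be classified as treatment emergent".

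**Recording period.** Protocol Section 9.8.8.2.2 says that adverse event reporting "continues up to 30 days after the last study treatment administration". Section 9.5 agrees: "All adverse events should be recorded for 30 days after last dose of study treatment". Neither sentence exempts open-label entrants. For one class of event there is no time limit: "Any SAE suspected to be related to the study treatment must be reported whenever it occurs".

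**Roll-over.** Protocol Section 3.1 lets subjects enter APD334-303 at disease worsening or after Week 52. Footnote t of the schedule in Protocol Appendix 1 provides blinded drug to cover a gap: "Study treatment may be dispensed at Week 52 if the subject qualifies for and has opted to participate in the APD334-303 OLE study". It makes a similar provision for subjects who become eligible before Week 52.

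**Tabulation.** SAP Section 5.6 analyses safety by treatment received. SAP Section 18.1.1 ends exposure time for subjects without the event at an undefined point: "to last participation for those who did not experience this AE". Section 18.1.6 plans comparative analyses of deaths, serious TEAEs, TEAEs leading to discontinuation, events of special interest, serious and opportunistic infections, and malignancies.

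**The concern.** A subject who goes straight from blinded treatment to open-label drug spends the 30 days after the last 308 dose on etrasimod. For a former placebo subject, those days include the first etrasimod dose ever taken. Any event recorded in 308 during that time passes the only date test in the SAP and is counted under placebo.

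At stake are the placebo rates in the comparative safety tables. Protocol Section 1.3 names first-dose bradycardia and AV block among events reported with this drug class, and SAP Section 18.1.5 makes bradycardia and AV conduction delay events of special interest. Etrasimod subjects who continue without a break have no initial first dose within 308, so first-dose events could enter the placebo column without a counterpart in the etrasimod column.

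The omission looks unintended. Section 18.1 has a counting rule for events that cross from APD334-302 into 308, and SAP Appendix 6 stops classifying rescue therapy once study treatment has ended. Nothing comparable covers adverse events crossing from 308 into APD334-303.

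**Working it through.** The plan gives no figure to reproduce. The check has two parts: trace one event through the rules, then size the possible overlap.

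**Tracing an event.** A placebo subject completes Week 52, takes bridging tablets, starts APD334-303 the day after the last of them, and has an event ten days later.
1. It falls within 30 days of the last 308 dose, so Protocol 9.8.8.2.2 puts it in the reporting period.
2. If it is entered in 308, its start date is later than the first 308 dose, so Appendix 2 flags it as a TEAE.
3. The treatment received in 308 was placebo, so it is tabulated as placebo.
4. In the exposure-adjusted rate it counts in the numerator. Whether time after roll-over counts for subjects without the event depends on the undefined end point.

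**Overlap per subject.** By the schedule, Week 12 is Day 85 and Week 52 is Day 365, so a completer has 365 − 85 + 1 = 281 treatment days.

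| Days on 308 treatment | 30 days relative to treatment time | 30 days as share of whole window |
|---|---|---|
| 281 | 30/281 = 10.7% | 30/311 = 9.6% |
| 84 | 30/84 = 35.7% | 30/114 = 26.3% |
| 28 | 30/28 = 107% | 30/58 = 51.7% |

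**Weight of one event.** Protocol Section 10.2 gives about 35 subjects and Section 6.1 a 2:1 allocation. If that ratio holds in Japan, the placebo arm is 35/3 ≈ 12, and one event is 1/12 = 8.3 points. SAP Section 6.5 says the ratio was not controlled there. With 8 placebo subjects the figure is 12.5 points, and with 16 it is 6.3.

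**Subject-years.** If all 12 complete and roll over directly, blinded placebo time is 12 × 281/365.25 = 9.2 and the overlap is 12 × 30/365.25 = 1.0.

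**Illustration of event counts.** Protocol Section 3.2 reports Phase 2 TEAE incidences of 56.0% (2 mg) and 50.0% (placebo). Assume these are 84-day risks with constant hazard h = −ln(1 − p)/84.
- Risk of at least one TEAE in 30 days = 1 − exp(−30h), which is 25.4% at the 2 mg rate and 21.9% at the placebo rate.
- With 12 placebo subjects rolling over and full capture, 12 × 0.254 ≈ 3 would have a TEAE in the overlap; with 6, about 1.5. Most of this comes from extra observation time. The part due to the change of drug is 12 × (0.254 − 0.219) ≈ 0.4 subjects.
- Etrasimod subjects who roll over gain the same 30 days, yet the contrast still narrows. With 84 days of treatment in each arm, incidence is 56.0% against 50.0%, a difference of 6.0 points. Adding 30 days at the 2 mg hazard to both arms gives 1 − exp(−0.821 − 0.293) = 67.2% against 1 − exp(−0.693 − 0.293) = 62.7%, a difference of 4.5 points.

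A constant hazard would understate any clustering just after a first dose.

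**The case against.** The strongest objection is that these events may never reach the 308 database. The 2-week and 4-week follow-up visits are only for subjects who do not enter the open-label study (Protocol Section 9.5). Events are elicited at visits (Section 9.8.8.2.1), and the schedule has no other 308 visit after Week 52 or early termination. SAP Sections 2.5 and 4 describe the analysis as one of APD334-308 data, Section 2.5 adding Week 16 to Week 52. This stands as a limit on likelihood. It does not close the gap: the reporting period has no open-label exception, events can be reported between visits, and SAP Section 6.4 summarises follow-up visits, so Week 52 is not a strict cut-off.

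The effect on inference is also limited. SAP Section 18 excludes between-group statistical comparisons of safety unless specified, and Section 18.1.5 leaves rate differences for events of special interest to the integrated analysis, whose plan is separate. In a study this small, a late event can be found in the listings by its date. All of this is fair, but Section 18.1.6 still specifies comparative analyses that use the flag.

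A reader might infer more than the documents support:
- **That placebo tables will contain open-label events.** The documents do not show this; it depends on data-entry rules not supplied.
- **That the same events are counted again in APD334-303.** Nothing supplied shows how that study counts events.
- **That a first-dose etrasimod effect in 308 is being diluted.** Etrasimod subjects enter 308 after 12 weeks of treatment, so there is no initial first-dose effect to dilute. The distortion would come from first-dose events added to placebo.
- **That open-label follow-up in general is swept in.** The protocol's 30-day limit bounds it, apart from later SAEs judged related.

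**Conclusion.** The gap is real, and its consequence is conditional. As written, the SAP would flag any event recorded in 308 after roll-over as a TEAE and, for a former placebo subject, tabulate it under placebo. Any such event inflates placebo rates and moves the comparison in etrasimod's favour. The undefined end of exposure time adds the risk that numerator and denominator use different cut-offs.

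The exposure is modest for completers and larger for subjects who leave early for disease worsening. The weight of one event rests on the assumed placebo arm of about 12. The event counts also assume Phase 2 rates, constant hazards, direct roll-over and full capture, so they show scale and do not predict what will happen. The point is worth correcting because the rule gives a wrong attribution when followed literally and the correction is small.

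**What to change.** In SAP Section 18.1, define the TEAE window as running from the first 308 dose to the earlier of (a) the last 308 dose + 30 days and (b) the first APD334-303 dose, excluding events that start or worsen on or after that open-label dose. Then:

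- Add the same end date to the Appendix 2 algorithm, and say how a partial date that could fall on either side of the first open-label dose is classified.
- Use it to define the end of participation in the exposure-adjusted rates of Section 18.1.1.
- List separately any event recorded in 308 that starts on or after the first APD334-303 dose.

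The cost is a short SAP edit and one merged date, the first APD334-303 dose; study conduct does not change. There is a small downside. Late events caused by blinded treatment that begin after open-label entry leave the 308 TEAE tables, as do related SAEs reported beyond 30 days. All remain visible in the listings.

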6.5. Blinding

This is a double-blind study with limited access to the randomization code. The study treatment and placebo tablets and bottles are identical in physical appearance. The treatment each subject receives will not be disclosed to the Investigator, study site staff, subject, Sponsor personnel involved with the conduct of the study (with the exception of the clinical supply staff and designated safety staff), or study vendors. The IWRS will hold treatment codes and bottle numbers for study treatment.

Treatment assignments should remain blinded unless that knowledge is necessary to determine subject emergency medical care. In case of an emergency, the Investigator has the sole responsibility for determining if unblinding of a subject's treatment assignment is warranted to provide appropriate medical care. Subject safety must always be the first consideration in making such a determination. The IWRS is programmed with blind-breaking instructions to guide the Investigator on how to obtain treatment assignment in the event of an emergency unblinding. The Investigator is requested to contact the Medical Monitor promptly in case of any treatment unblinding. If a subject's treatment assignment is unblinded, the Sponsor must be notified within 24 hours after breaking the blind. The date and reason the blind was broken must be recorded in the source documentation and eCRF, as applicable.

For Suspected, Unexpected, Serious Adverse Reactions, the Sponsor's Pharmacovigilance designee responsible for managing SAEs will access the IWRS to obtain the subject's treatment assignment for the purpose of regulatory reporting.

Subjects who are unblinded may be eligible to enroll into the OLE study (Section 5.1.1).

During the clinical conduct of Study APD334-308, the Sponsor may lock and unblind Study APD334-302 for regulatory filings outside of Japan. Prior to unblinding Study APD334-302, a data disclosure plan will be finalized which will provide such details as access to and disclosure of treatment information, as well as description of the structure and process of blinded and unblinded study teams.

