18.1.1.1. Severity

Severity is classified as Grade 1: Mild, Grade 2: Moderate, Grade 3: Severe, Grade 4: Life Threatening, Grade 5: Death Related to AE, using the Common Terminology Criteria for Adverse Events, version 5.0 (CTCAE v5.0).

All TEAEs will be summarized by SOC, PT, and maximum severity, with SOC and PT presented by descending frequency. If a subject reports a TEAE more than once within a SOC/PT, the AE with the worst-case severity will be used in this summary.

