18.1.2. TEAEs Leading to Discontinuation of Study Treatment

TEAEs leading to discontinuation of study treatment will be identified by action taken being recorded as “Drug withdrawal” on the Adverse events eCRF.

All TEAEs leading to discontinuation of study treatment will be summarized by SOC and PT. A listing of all TEAEs leading to discontinuation of study treatment will also be presented.

Liver-related AEs are defined by either SOC of hepatobiliary disorders or PT of alanine aminotransferase abnormal, alanine aminotransferase increased, aspartate aminotransferase abnormal, aspartate aminotransferase increased, hepatic enzyme abnormal, hepatic enzyme increased, liver function test abnormal, liver function test increased, transaminases abnormal, or transaminases increased.

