18.1.3. Serious and Non-Serious TEAEs

Serious adverse events (SAEs) are those events recorded as “Serious” on the Adverse Events page of the eCRF. A summary of serious TEAEs by SOC and PT will be prepared.

All serious TEAEs will be summarized by SOC and PT. If the seriousness is missing, the AE will be considered as “Serious” for the summary tabulation purpose only. A serious TEAE listing will also be presented. All non-serious TEAEs will also be summarized by SOC and PT.

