18.1.4. TEAEs Leading to Death

TEAEs leading to Death are those events which are recorded with an outcome as “Fatal” on the Adverse Events eCRF. A listing of TEAEs leading to death will be presented.

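### An adverse event carried over from APD334-302 that leads to drug withdrawal or interruption, or becomes serious, without a grade increase is left out of the APD334-308 safety summaries

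*SAP*

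**What the plan says.** SAP Section 18.1 defines TEAEs in this study: they "are defined as AEs that started or worsened in severity on or after the first dose of study treatment in Study APD334-308". For events that straddle the two studies it adds: "An event that was on-going at end of APD334-302 will be reported in APD334-308 only if it became worsened (increase in severity") after that dose. It also says that an integrated report on both studies will count such an event a single time.

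SAP Appendix 2 programs the same rule. With a known start date, "If start date < study drug first dose date in APD334-308, then not TEAE"; the only exception is a later increase in severity.

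The summaries of consequences then apply the TEAE filter:

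- Section 18.1.2: "All TEAEs leading to discontinuation of study treatment will be summarized by SOC and PT".
- Section 18.1.3: "All serious TEAEs will be summarized by SOC and PT".
- Section 18.1.6: the overview lines for serious events, discontinuation and interruption are all TEAE lines. The comparative analyses include serious TEAEs and TEAEs leading to discontinuation of treatment.

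Protocol Section 10.12.2 commits to the incidence of adverse events, serious adverse events and adverse events leading to discontinuation. That sentence does not limit them to treatment-emergent events. SAP Section 3.3, which lists changes from the protocol, does not mention a narrowing.

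**The concern.** Severity, seriousness and action taken are separate attributes of an adverse event. The rule lets only the first bring a carried-over event into the APD334-308 tables. Yet a subject may tolerate an event through Week 12, roll over, and stop treatment in APD334-308 because it persists. The grade has not changed, so the event does not qualify, and the withdrawal it caused does not appear among AE-related discontinuations.

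The study's safety objective (protocol Section 2.3) is long-term safety up to 52 weeks. Withdrawals, interruptions and serious events are the main tolerability counts for that objective, and in a study of this size each one is visible as a percentage. The disposition summary (SAP Section 10) counts reasons for stopping treatment with no TEAE filter, so the same report could show an AE withdrawal in one table that is missing from another.

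**Working it through.** The plan gives no figure on this point, so the check is to trace one kind of event through the outputs: onset in APD334-302, ongoing at the first APD334-308 dose, no later grade increase.

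**Step 1. Is it a TEAE in APD334-308?** No, under both Section 18.1 and Appendix 2.

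**Step 2. Can it lead to withdrawal or interruption without a grade change?** Yes. Protocol Section 5.1 allows treatment to be stopped for any adverse event on the judgement of the Investigator or Medical Monitor. One of its liver criteria is met when a transaminase level persists above a threshold for more than 2 weeks, so duration alone can trigger it. Protocol Section 6.3.2 lets the Investigator withhold treatment when judged necessary. None of these needs a rise in grade. The event is then absent from the Section 18.1.2 table and from the Section 18.1.6 discontinuation or interruption lines.

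**Step 3. Can it become serious without a grade change?** Yes, but in fewer cases. Protocol Section 9.8.8.1.5 defines Grade 3 partly by hospitalisation, disability and medical significance, so a Grade 1 or 2 event that meets one of those criteria would normally rise. Two routes remain:

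- an event already at Grade 3 or 4 at roll-over that later meets a seriousness criterion;
- a criterion not tied to grade. For example, protocol Section 9.8.8.3.1 makes even an elective hospitalisation serious if the condition was not preexisting.

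Such an event is absent from the Section 18.1.3 table and the serious-TEAE comparison.

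**Step 4. Where else could the consequence be counted?**

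| Output | Does it supply the missing count? |
|---|---|
| Disposition, SAP Section 10 | Counts the treatment stop and its reason, but not by SOC and PT |
| Listing of all AEs, SAP Section 18.1.1 | A listing, not an incidence; whether the event reaches it depends on how the Section 18.1 wording on reporting is read |
| UC-related hospitalisations, SAP Section 17 | Yes, for that kind of hospitalisation only |
| Integrated report, SAP Sections 4 and 18.1 | Counts the event once; nothing says that the later seriousness or action taken is carried onto the record |
| APD334-302 report | Unknown. Protocol Section 6.5 says "the Sponsor may lock and unblind Study APD334-302 for regulatory filings outside of Japan" while APD334-308 is running, and does not say how ongoing events are updated |

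**Step 5. Size of one omission.** Inputs: about 35 subjects (protocol Section 10.2) and 2:1 allocation (protocol Section 6.1).

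- Etrasimod: 35 × 2/3 = 23.3, about 23. Placebo: 35 × 1/3 = 11.7, about 12.
- Step per omitted subject = 100/n. Etrasimod: 100/23 = 4.3 points. Placebo: 100/12 = 8.3 points.
- Two omitted subjects: 200/23 = 8.7 points or 200/12 = 16.7 points.
- Illustration only: if 3 of 23 etrasimod subjects withdrew for adverse events and 2 of those events were carried over at an unchanged grade, the table would show 1/23 = 4.3% instead of 3/23 = 13.0%.

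The 23/12 split is an assumption. Protocol Section 10.2 says only that parent-study subjects may be eligible, and SAP Sections 6.5 and 8.2 say that the central randomisation did not control allocation in Japan. If fewer enrol, each step is larger. The documents give no expected frequency of such events.

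**The case against.** The best defence is that the gap is narrow and other outputs cover much of it.

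- **Deaths.** A reader might infer that fatal events are lost too, since Section 18.1.4 says "A listing of TEAEs leading to death will be presented". They are not. Severity includes "Grade 5: Death Related to AE, using the Common Terminology Criteria for Adverse Events, version 5.0", so a carried-over Grade 1 to 4 event that proves fatal has increased in severity and is a TEAE. Deaths also have a listing in Section 18.2 and a comparative line in Section 18.1.6 without the TEAE label.
- **Counted in neither study.** This is also tempting, and the documents do not establish it. An event that began after the first APD334-302 dose belongs to that study, and the integrated report counts it once. What has no stated home is the later consequence. The APD334-302 SAP and the integrated analysis plan might supply one, but they are not among the documents.
- **Loss from the database.** Section 18.1.1 lists all adverse events whether or not they are treatment-emergent. Appendix 2 has a branch that classes earlier-onset events as not TEAEs, which suggests that such records are in the dataset. The Section 18.1 sentence may therefore govern counting only. That is plausible, but the SAP should say so.
- **Uncertain timing.** Protocol Section 9.8.8.1.5 asks for severity at onset and maximum severity, so the date of a rise may be unclear. Section 18.1 treats an event as treatment-emergent when its status cannot be decided, which would bring some cases back. It does not help where the grade plainly did not change.
- **Intended TEAE scope.** The sentence before the protocol's commitment in Section 10.12.2 concerns TEAEs, so the restriction may have been meant throughout. Even so, the commitment itself names adverse events and serious adverse events.

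These points limit the concern. None puts a same-grade carried-over withdrawal into the discontinuation table.

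**Conclusion.** The concern holds in a limited form. If the SAP is followed exactly, an event carried over from APD334-302 that leads to withdrawal or interruption in APD334-308 at an unchanged grade, or becomes serious without a grade rise, is left out of the corresponding summaries. For withdrawals and serious events it is also left out of the comparative analyses. This is narrower than protocol Section 10.12.2 and can make the AE and disposition tables disagree. For serious events the gap is chiefly those already at Grade 3 or 4 and criteria not tied to grade.

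On the assumed 23/12 split, each omission understates an incidence by about 4.3 or 8.3 points. Whether any such case occurs is unknown.

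A reader might infer that the rule makes etrasimod look better tolerated. The documents do not support a direction: the rule is the same in both arms, the step per subject is larger on placebo, and nothing shows that same-grade carried-over events with these consequences would be more common on etrasimod.

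**What to change.** Before unblinding, amend the SAP as follows.

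1. In Sections 18.1.2, 18.1.3 and 18.1.6, tabulate also any adverse event whose drug withdrawal, interruption or seriousness criterion occurs on or after the first APD334-308 dose, whichever study it began in. Flag those with onset in APD334-302. A separate table of carried-over events with new consequences would also do.
2. In Section 18.1, state that the worsening rule decides TEAE status only, and that every event ongoing at roll-over stays in the APD334-308 AE dataset and listings.
3. State that the integrated analysis carries the updated seriousness and action taken onto the event, which is still counted once.

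The fatal-event output needs no change on this account. The cost is SAP wording, a dataset flag and a little programming. Some safety percentages may become slightly less favourable.
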